4.4 Participant Withdrawal

Each participant must be informed that participation in the trial is voluntary and that he/she may withdraw from the trial at any time and that withdrawal of consent will not affect his/her subsequent medical treatment or relationship with the treating clinician. The investigator(s) or sponsor may withdraw participants from the trial only if indicated by safety/clinical issue or trial protocol. Participants that discontinue azithromycin will not repeat the HROM trial but will be asked to complete all other trial processes such as questionnaires and spirometry if they are willing and have consented to do so. Participants who decline a second HROM trial after their initial trial will be asked to complete all other trial processes if they are willing and have consented to do so.

Participants should remain in the trial for follow-up unless they request to fully withdraw. All data up to the point of withdrawal should be stored. Participants who choose to withdraw or who complete will be invited to complete a short anonymous survey (Appendix B: Trial Experience Survey) to determine their experience of trial participation and any reasons for withdrawal.

In the event of participant withdrawal, the investigator(s) will promptly explain to the participant that their involvement in the trial will discontinue and explain why. The patients' treating clinician will provide medical treatment and/or other necessary measures deemed appropriate by the usual clinician or the participant. This information will be recorded in the CRF. If a participant loses capacity to consent to trial procedures during the trial period, they will be withdrawn from the study. Any data already collected from their participation may be used in the final analysis.

Participants who discontinue early from the trial treatment and/or follow-up will do so for one of the following primary reasons: AE(s), participant deterioration of disease, participant death, lost to follow-up, participant withdrew consent, significant protocol violation. Trial discontinuation information will be documented on the participants CRF.

5. TRIAL ASSESSMENTS

5.1 Summary

Participants who fulfil all eligibility criteria and present no contraindications will be observed for 28 days (up to 42 days) on their azithromycin treatment as part of usual care as decided by their treating clinician. Participants will be advised to continue to take all other usual treatments as instructed by their treating clinician.

Participants will be encouraged to comply with other usual treatments of their respiratory disease, including inhaled and oral medications, throughout the duration of the study.

5.2 Assessment Fidelity

Any deviation from the protocol regarding azithromycin treatment, either curtailment or inconsistent administration of treatment, will result in exclusion from analysis.

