6. OUTCOMES AND MEASURES

6.1 Feasibility outcomes

This study's primary outcomes will be the feasibility and acceptability outcomes, these include:

- Recruitment: eligibility to consent ratio, recruitment rate, and participant retention to followup.
- Data quality: Completion of clinical outcomes at follow-up and patterns of missing data for the trial measures. Completion of participant symptom questionnaires throughout the study. Completion of trial processes, principally HROM.
- Acceptability of assessment: Quantify the proportion of participants who judge the trial investigations, principally HROM, to be acceptable.

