11. STATISTICAL METHODS

The primary feasibility outcomes will consist of recruitment rate, retention rate, adverse events, compliance, and acceptability of the HROM assessment. The recruitment rate, consisting of the eligibility and consent rate will be calculated with 95 % confidence intervals (CI). A table showing baseline demographic and clinical characteristics for each group will be presented to indicate any differences between groups. Participant characteristics will be summarised using appropriate statistics. Medians (IQR) will be reported for ordinal data, mean (standard deviation) for continuous data and raw count (number (%) will be reported for nominal data.

For the clinical outcomes, all HROM data will be recorded, and median metrics will be recorded for the overall participant cohort and will be broken down into smaller categories based on primary respiratory diagnoses. Questionnaire data will be reported for all participants and mean scores will be reported. A table showing baseline demographic and clinical characters will be presented. Participant characteristics will be summarised using appropriate statistics. Medians (IQR) will be reported for ordinal data, mean (standard deviation) for continuous data and raw count (number [%]) will be reported for nominal data.

Comparison of baseline and follow-up HROM and questionnaire data will be made using paired ttests for normally distributed data and Mann-Whitney U testing for skewed data. Averages of all

HROM metrics and questionnaire data will be presented in tables and p-values of the statistical tests will be displayed alongside this data.

Safety data will be summarised using descriptive statistics.

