13.3 Discontinuation/Withdrawal of Participants from Study

Each participant has the right to withdraw from the study at any time. In addition, the investigator may discontinue a participant from the study at any time if the investigator considers it necessary for any reason including:

Pregnancy

- Ineligibility (either arising during the study or retrospective having been overlooked at screening)
- Significant protocol deviation
- Significant non-compliance with treatment regimen or study requirements
- An adverse event, which requires discontinuation of the study medication or results in an inability to continue to comply with study procedures
- Consent is withdrawn
- Lost to follow up
- Loss of participant mental capacity to follow the trial protocol

If the participant withdraws consent, no further trial activity will occur, and any samples will be destroyed and the reason for withdrawal will be recorded in the CRF.

As part of the consent process the participant will be asked if all data collected up until the time of withdrawal can be used as part of the study results. If the participant is withdrawn due to an adverse event, the investigator will arrange for follow-up visits or telephone calls until the adverse event has resolved or stabilised. Their data may still be used for analysis.

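### Section 5.2 excludes participants with curtailed or inconsistent azithromycin from an unnamed analysis, which can bias the primary feasibility and safety summaries and is at odds with Sections 4.4 and 13.3

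*Protocol*

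**What the plan says.** Section 5.2 (Assessment Fidelity) consists of one sentence: "Any deviation from the protocol regarding azithromycin treatment, either curtailment or inconsistent administration of treatment, will result in exclusion from analysis". It names no outcome and gives no threshold.

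Section 11 opens: "The primary feasibility outcomes will consist of recruitment rate, retention rate, adverse events, compliance, and acceptability of the HROM assessment". Section 6.1 also sets out the primary outcomes: "This study's primary outcomes will be the feasibility and acceptability outcomes, these include". Its first item is "Recruitment: eligibility to consent ratio, recruitment rate, and participant retention to followup". Its second is data quality, meaning completion of outcomes at follow-up, patterns of missing data, and completion of trial processes, chiefly HROM. Adverse events and compliance appear as primary only in Section 11.

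Section 4.4 deals with people who stop the drug: "Participants that discontinue azithromycin will not repeat the HROM trial but will be asked to complete all other trial processes", and "Participants should remain in the trial for follow-up unless they request to fully withdraw". Section 13.3 lists an adverse event requiring the study medication to be stopped among the reasons for discontinuing a participant. Of those withdrawn for an adverse event it says: "Their data may still be used for analysis". The same list refers to significant non-compliance, whereas 5.2 refers to any deviation.

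The synopsis plans 30 participants without a formal sample size calculation.

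**The concern.** A feasibility study has to count the people for whom things did not go to plan. A rule that removes participants because they stopped or took the drug irregularly conditions the denominator on the behaviour being measured. If it reaches the primary summaries, compliance becomes circular, adverse events that led to stopping drop out of the safety summary, and the missing-data picture looks cleaner than it was. A later trial would be planned on those figures.

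The exploratory before/after comparison is affected too. There is no control group, so the mean symptom change would describe only those who tolerated and adhered to azithromycin. Data from the others would have been collected under Section 4.4 and then left out.

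**Working it through.** **Inputs.** N = 30 (synopsis, sample size rationale). The protocol gives no expected non-adherence, loss or adverse-event rate, so all such numbers below are assumptions. The planned 30 rests on no calculation, so there is no figure of the plan to reproduce. Intervals are exact (Clopper-Pearson) 95%.

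**Compliance, if it means azithromycin compliance.** With k non-adherent, the result in everyone is (30 − k)/30. Under 5.2 it is (30 − k)/(30 − k), which is always 1.

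| k (assumed) | All 30 | After 5.2 |
|---|---|---|
| 3 | 27/30 = 90% (73.5–97.9) | 27/27 = 100% (87.2–100) |
| 6 | 24/30 = 80% (61.4–92.3) | 24/24 = 100% (85.8–100) |
| 9 | 21/30 = 70% (50.6–85.3) | 21/21 = 100% (83.9–100) |

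**HROM completion and missing data.** Section 4.4 gives those who stop no second HROM. If 6 stop and the other 24 complete both tests, completion is 24/30 = 80% in everyone and 24/24 = 100% after 5.2. This follows from Section 6.1 alone and does not depend on what compliance means.

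**Adverse events.** Assume 10 of 30 have an event (33.3%) and two thirds of the non-adherent stopped because of one. After exclusion:
- k = 3: (10 − 2)/27 = 8/27 = 29.6%
- k = 6: (10 − 4)/24 = 6/24 = 25.0%
- k = 9: (10 − 6)/21 = 4/21 = 19.0%

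**Retention.** Stopping the drug is not leaving the trial, so the effect depends on who is lost. With k = 6:
- All 30 attend follow-up: 30/30 in everyone, 24/24 after 5.2. No distortion.
- Four of the 6 are lost and nobody else: 26/30 = 86.7% (69.3–96.2) against 24/24 = 100% (85.8–100). Inflated.
- All 6 attend and 2 adherent participants are lost: 28/30 = 93.3% against 22/24 = 91.7%. Slightly deflated.

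**Exploratory paired change.** The 95% half-width is t(0.975, n − 1)/√n, in standard deviations of the change. It is 0.373 for n = 30 and 0.422 for n = 24. The loss of precision is modest; selection of the analysed set matters more.

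**Can 5.2 be read as covering only the HROM comparison?** For participants who stop, Section 4.4 already rules out the second HROM, so there is no HROM pair left to exclude. For them 5.2 can only remove questionnaire, spirometry, cough, missing-data and safety information, most of which Section 4.4 asks them to go on providing.

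**The case against.** The best defence is that 5.2 was never meant to reach the primary outcomes. Its heading concerns assessment fidelity, it stands directly before the HROM procedure, and other text assumes that non-completers are counted: missing-data patterns are an outcome in 6.1, Section 9.1.2 has all adverse events recorded, and the synopsis has them listed and summarised. An adherent set is also defensible for an exploratory mechanistic question. This is a plausible account of intent, but 5.2 does not say it, and it does not help those who stop the drug, as shown above. An analysis plan could define sets and thresholds, but it would have to override this sentence to repair it.

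Several stronger readings that a reader might infer are not supported:
- *The primary outcomes become unusable.* Eligibility, consent and recruitment rates are untouched. Acceptability comes from experience surveys, and the end-of-trial survey is anonymous, so answers could not readily be removed by adherence. Retention and adverse-event rates remain computable, though open to bias.
- *Everyone who stops counts as not retained.* Section 4.4 keeps them in follow-up.
- *Compliance is certain to be 100%.* Section 11 does not say compliance with what. If trial procedures are meant, the figure may be biased but is not fixed.
- *One missed dose triggers exclusion.* The text speaks of inconsistent administration and sets no number.
- *Sections 4.4 and 13.3 flatly contradict 5.2.* Section 4.4 requires collection, not analysis. Its sentence "Any data already collected from their participation may be used in the final analysis" concerns loss of capacity only. Section 13.3 is permissive.
- *The symptom result must be biased towards benefit.* Selection on tolerance makes that likely, but nothing in the protocol quantifies it.

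**Conclusion.** Section 5.2 is wrong as written and should be corrected. Its unlimited exclusion makes azithromycin compliance 100% whatever happens, against 90%, 80% or 70% if 3, 6 or 9 of 30 are non-adherent. It removes adverse events in those who stopped because of them (33.3% falling to between 29.6% and 19.0% under the stated assumptions) and part of the missing-data pattern that Section 6.1 makes primary. Retention is inflated only to the extent that the excluded are also the lost. The symptom change is restricted to people who tolerated and adhered to the drug.

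The conflict with Section 4.4 is one of purpose: data are collected that 5.2 then bars from use. With Section 13.3 it is partial: a participant withdrawn because an adverse event stopped the drug is excluded by one section and may be analysed under the other, and the two sections use different degrees of non-compliance. The direction for compliance is certain under the azithromycin reading. The sizes rest on assumed counts.

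**What to change.** Reword Section 5.2 and align Sections 4.4, 11 and 13.3 with it:

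- Include all consented participants in the feasibility, acceptability and safety summaries, whatever their azithromycin adherence.
- Analyse change in symptoms, spirometry and cough in all participants with data at both visits, regardless of adherence.
- Report HROM change in those with both tests. Count participants not offered the second test because azithromycin stopped separately from those who declined it.
- Limit the 5.2 exclusion to a secondary on-treatment analysis of the exploratory outcomes, based on the treatment information recorded in the CRF.
- Say in Section 11 what compliance refers to, and make the primary outcome lists in Sections 6.1 and 11 agree.

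The cost is a wording amendment. The main analyses need no new visits or measurements. The on-treatment set depends on how fully the CRF captures azithromycin use, since the schedule of assessments lists no separate adherence measure. The compliance and symptom results may look less favourable than under the present rule.

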5.3 High-resolution oesophageal manometry protocol

All participants will be investigated using a standardised HROM technique. Participants will be advised to fast 4 hours prior to investigation and will be investigated with a 36-channel combined

manometric and impedance monitoring catheter. This catheter will be inserted trans-nasally to a length of 60cm from the nostril. Participants will then be asked to lay supine for 5 minutes prior to measurement.

A standardised protocol of oesophageal function tests will be followed, with further tests utilised if felt appropriate by the clinical scientist performing the test. The mandatory tests include:

- 10 separate swallows of 5mls of water with an interval of 15 seconds between each swallow.
- The participant will then be asked to complete 5 rapid swallows, ingesting 2mls of water at each swallow.
- The final test will consist of the participant swallowing 5 small pieces of white bread in 5 separate swallows.

Each trial will be analysed manually by an expert gastrointestinal physiologist and a full analysis report will be produced each individual trial in each participant.

6. OUTCOMES AND MEASURES

6.1 Feasibility outcomes

This study's primary outcomes will be the feasibility and acceptability outcomes, these include:

- Recruitment: eligibility to consent ratio, recruitment rate, and participant retention to followup.
- Data quality: Completion of clinical outcomes at follow-up and patterns of missing data for the trial measures. Completion of participant symptom questionnaires throughout the study. Completion of trial processes, principally HROM.
- Acceptability of assessment: Quantify the proportion of participants who judge the trial investigations, principally HROM, to be acceptable.

6.2 HROM Testing Measures

The following HROM test variables will be assessed:

- Distal Contractile Integral: The average DCI from the 10 liquid swallows will be collected and will be used to quantify the vigour of oesophageal contraction.
- Integrated Relaxation Pressure: The average IRP4sec is defined as the average minimum oesophagogastric junction pressure for 4 seconds of relaxation and will be ascertained by the collecting the average measurement over the 10 liquid swallows. This will give a quantification of the adequacy of relaxation at the oesophagogastric junction.
- Lower Oesophageal Sphincter Resting Pressure: Basal and relaxation LOS pressure measurements will be taken, and the LOS Resting Pressure will be measured for all participants.
- Chicago Classification: Using Version 4.0 of the Chicago Classification we will provide each
 participant with a manometric diagnosis. These diagnoses include: Normal Motility,
 Ineffective Oesophageal Motility, Absent Contractility, Achalasia, EGJ Outflow Obstruction,
 Hypercontractile Oesophagus, and Distal Oesophageal Spasm. Participants will receive a
 classification at baseline and at follow-up.
- Presence of a Hiatus Hernia: All HROM examinations will be analysed for likelihood of the presence of a hiatus hernia.

6.3 Symptom Burden Measures

In this study, we will measure symptom burden broadly with general symptom scores on cough, sputum production, breathlessness, and symptoms associated with airway reflux. We will also assess disease-specific symptom burden for the participants' diagnoses.

6.3.1 Hull Airway Reflux Questionnaire

- All participants included in the trial will be assessed with the HARQ, a validated tool for assessing symptoms of reflux, at screening, baseline (pre-treatment), and follow-up (post-treatment).Participants successfully enrolled on the trial will have an abnormal HARQ score of ≥14. We will compare the differences between participants at baseline and follow-up and correlate this to their HROM findings.

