Exclusion Criteria	 Previous treatment with long-term macrolides in the past 3 months. Unable to be investigated with HROM due to contraindications such as anatomical abnormalities or diseases of the oesophagus or unwilling/unable to be investigated with HROM based on the clinical judgement of the investigators due to severity of lung disease. Have another cardiorespiratory cause for their symptoms (such as heart failure or lung cancer). Are unable or unwilling to consent to or complete the trial procedures. Women of child bearing potential not using effective means of contraception. Effective methods of contraception include any oral contraceptive pill, any intrauterine device, any long term contraceptive implant, and any long-acting contraceptive injection Have been involved in another medicinal trial (CTIMP) within past four weeks.

Trial Treatment(s)	Trial Participants will be commenced on azithromycin therapy as part of usual clinical care.
Trial Endpoints and Statistical Methods	For trial endpoints, appropriate statistical analysis will be performed to compare HROM metrics and symptom questionnaire data at baseline and at follow-up.
	A table showing baseline demographic and clinical characteristics for each group will be presented. Participant characteristics will be summarised using appropriate statistics. Medians (interquartile range) will be reported for ordinal data, mean (standard deviation) for continuous data and raw count (number, %) will be reported for nominal data.
	For participant outcome data, descriptive statistics, mean (standard deviation) for continuous outcomes and raw count (%) for categorical outcomes, will be reported for each group at baseline and at 1-month follow-up, and for continuous objective and subjective cough data where applicable.
Safety Analyses	AEs/SAEs will be listed and summarized using descriptive statistics.
Sample Size Rationale	As this is a pilot study, a formal sample size calculation has not been performed. We will recruit 30 participants over 12 months based on National Institute for Health Research recommendations for pilot/feasibility studies.

SCHEDULE OF ASSESSMENTS AND PROCEDURES

Visit	Screening Visit	Baseline visit		Follow up visit
Day	-28 to -7	0		28 to 42
Procedure/Assessment			mi i	
Written Informed Consent	Х			
Inclusion/ Exclusion Criteria	Χ	Х		
Invitation Experience survey	Χ			
Setup of the Hyfe Cough Tracker©	Χ			
Monitoring of cough frequency using the Hyfe Cough Tracker©	X**	Х		Х

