Vital signs		Х	apy	Х
Weight and Height		Х	her	Х
Physical Examination		Х	n t	Х
Electrocardiogram		Х	yci	Х
Past Medical History		Х	m	
Review of previous laboratory results		Х	ᆴ	
AE Monitoring		Х	azi	Х
			0	
MRC Dyspnoea grade		X	n t	X
Hull Airway Reflux Questionnaire	Х	Х	om [Х
Breathlessness, Cough, and Sputum Scale		Х	Minimum 1 month on azithromycin therapy	Х
St George's Respiratory Questionnaire		Х	ן שַׁ ן	Х
Leicester Cough Questionnaire		X*	i	X*
King's Brief Interstitial Lung Disease Questionnaire		X*	Σ	Χ*
COPD Assessment Test		X*		X*
Asthma Control Questionnaire		X*		X*
Visual Analogue Scales (Cough)		Х		Х
Numeric Rating Scale (Breathlessness)		Х		Х
Spirometry		Х		Х
High-Resolution Oesophageal Manometry†		Х	 	Х
Health Care Utilisation				Х
Evaluation of usual care received				Х
Trial Experience Survey				Х

^{*}Questionnaires will be administered dependent on patients' main respiratory diagnosis.

^{**}If willing, patients would have the possibility to begin objective unobtrusive continuous cough monitoring after the screening visit.

[†]Patients will be eligible if they have had HROM performed up to 3 months prior to screening, however they must not have been treated with macrolide antibiotics during this time.

TRIAL FLOW CHART

Day -28 to -7

[figure not shown]
Consent
Inclusion/Exclusion Criteria
Invitation Experience Survey
Hull Airway Reflux Questionnaire
Setup of Hyfe Cough Tracker© equipment and
download of Hyfe Research© smartphone app

Day 0

Inclusion/Exclusion Criteria
Hull Airway Reflux Questionnaire
Physical Examination
Vital Signs
Spirometry
ECG
HROM
Past Medical History
Questionnaires as per schedule and based on patients primary diagnosis
Review of Hyfe Research© app data

Day 28-42

Inclusion/Exclusion Criteria
Hull Airway Reflux Questionnaire
Physical Examination
Vital Signs
Spirometry
HROM
ECG
Past Medical History
AE Monitoring
Questionnaires as per schedule and based on patients primary diagnosis
Review of Hyfe Research© app data

LIST OF ABBREVIATIONS

Define all unusual or 'technical' terms related to the trial. Add or delete as appropriate to your trial. Maintain alphabetical order for ease of reference.

AE Adverse Event

AECOPD Acute Exacerbation of COPD

AR Adverse Reaction

CA Competent Authority

CC Chronic Cough

COPD Chronic Obstructive Pulmonary Disease

CRF Case Report Form

CTA Clinical Trial Authorisation

CTIMP Clinical Trial of Investigational Medicinal Product

DSUR Development Safety Update Report

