4.1 Inclusion Criteria

- Males and females aged ≥18 years.
- Have a diagnosis of chronic respiratory disease (COPD, asthma, interstitial lung disease, chronic cough, cystic fibrosis, and/or bronchiectasis) confirmed by a consultant respiratory physician.
- Exhibit symptoms consistent with airway reflux, demonstrated by a score ≥14 on the Hull Airways
 Reflux Questionnaire.
- Are being initiated on azithromycin treatment as part of routine clinical care by their usual clinician. This will include all common treatment regimes, 250mg once daily, 250mg three times per week, and 500mg three time per week.
- Are willing and able to consent to all trial procedures.

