4.3 Participant Identification and Screening

All patients attending the Hull University Teaching Hospitals NHS Trust (HUTH) respiratory medicine outpatient department for management of their chronic respiratory disease and are being considered for long-term treatment with azithromycin will be considered suitable for participation. Respiratory medicine clinicians and specialist nurses working within the trust will be trained and instructed in the recruitment procedure and any patients who may meet the eligibility criteria will be referred to the trial team and contacted, with the patients' consent and after given time to consider participation and ask questions, for screening to assess eligibility to participate in the study.

Participants expressing an interest in the trial will be provided with a participant information sheet and informed consent will be obtained. All eligible patients who are approached for the trial will be invited to complete a short anonymous questionnaire (Appendix: Trial Invitation Experience Survey) assessing their experience of recruitment and why they consented to participate or declined.

Participants that fail screening can be re-screened (to a maximum of 3 times) if the reason for screen failure is resolved prior to completion of trial recruitment. Participants entering the trial following re-screening after an earlier failed screening will be allocated a new trial ID and have their earlier trial ID and the reason for initial screen failure recorded in their CRF and the Participant Master Index.

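### Repeating the eligibility review at Day 0 can truncate the HARQ analysis baseline at 14 and build regression to the mean into HARQ change; the flow chart and Schedule also disagree on eligibility at follow-up

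*Protocol*

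**What the plan says.** - **Entry.** Section 4.1 requires of each participant: "Exhibit symptoms consistent with airway reflux, demonstrated by a score ≥14 on the Hull Airways" (the questionnaire's name continues on the next line). It does not name the visit whose score counts. Section 6.3.1 adds that enrolled participants "will have an abnormal HARQ score of ≥14". Section 4 makes anyone who does not meet every inclusion criterion ineligible.
- **Measurement.** Section 6.3.1 has the HARQ taken "at screening, baseline (pre-treatment), and follow-up (post-treatment"). The baseline-to-follow-up difference is then compared and correlated with the HROM findings.
- **Eligibility review.** The Schedule of Assessments marks "Inclusion/ Exclusion Criteria" at screening and at Day 0, and not at follow-up. The Trial Flow Chart lists "Inclusion/Exclusion Criteria" at screening, at Day 0 (directly above the HARQ) and again at Day 28-42.
- **Visit lists.** Section 7.3 puts the HARQ under the eligibility assessment at screening. Section 7.4 (Day 0) lists a HARQ but no eligibility review. Section 7.5 (follow-up) lists no eligibility review.
- **Analysis.** There is one group. Section 11 compares baseline with follow-up questionnaire data, by paired t-test when normally distributed, and reports p-values. Section 6.1 makes feasibility and acceptability the primary outcomes.

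**The concern.** When a noisy score must exceed a threshold to be accepted, and that same score is the baseline, the accepted baselines are too high on average. The next measurement falls back towards the patient's usual level even if treatment does nothing. A control arm would show the same fall and cancel it; here there is none.

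The design already holds the usual protection, a HARQ at screening separate from the one at Day 0. If only the screening score decides entry, selection acts on that score's error and the Day 0 value is free of it. Re-applying the threshold at Day 0 gives this up.

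At stake are the HARQ change, its p-value, and the planned correlation of HARQ change with HROM findings. This is a rule about who enters, so an analysis plan written later cannot fully undo it.

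The flow-chart entry at Day 28-42 raises a second, smaller matter. By then HARQ is an outcome, and an entry threshold on it has no proper role.

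**Working it through.** **No figure to reproduce.** The sample of 30 has no formal calculation, and the protocol gives no HARQ mean, SD, reliability or expected change. The protocol supplies only the threshold (14), the three measurement times, the single group, the paired comparison and n = 30. Everything else below is assumed.

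**Model.** Observed HARQ = stable true score + independent normal error at each visit. SD is the between-patient SD of the observed score in referred patients, rho the test-retest correlation, and c = (14 − mean)/SD. The true treatment effect is zero.

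**Closed form for a threshold on the baseline value alone.** Spurious fall = (1 − rho) × SD × φ(c)/(1 − Φ(c)).

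Example with mean 20, SD 12, rho 0.7:
- c = (14 − 20)/12 = −0.5
- φ(c)/(1 − Φ(c)) = 0.352/0.691 = 0.509
- fall = 0.3 × 12 × 0.509 = 1.8 points

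With thresholds at both screening and Day 0 the fall is smaller than this, because those who pass the first have higher true scores. That case was simulated.

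**Simulated fall from Day 0 to follow-up, in points (SD 12 to 13, rho 0.7 to 0.8):**

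| Assumed referred mean | Screening score only | Screening and Day 0 | Share of screening-qualified patients with Day 0 HARQ below 14 |
|---|---|---|---|
| 15 to 20 | about 0 | 0.8 to 2.0 | 13% to 24% |
| 30 | about 0 | 0.3 to 0.6 | 5% to 6% |

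**Wider range, in SD units, with both thresholds.** Ranges run over rho 0.9 down to 0.6. Type I error is for a two-sided 5% paired t-test (level assumed) at n = 30.

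| c | Spurious fall (SD) | Type I error |
|---|---|---|
| −2 | 0.003 to 0.02 | about 5% |
| −1 | 0.02 to 0.09 | 5% to 8% |
| 0 | 0.05 to 0.23 | 8% to 30% |
| 0.5 | 0.07 to 0.31 | 12% to 51% |

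With the screening score alone deciding entry, the fall is about 0.00 SD and type I error 4.5% to 5.5% at every setting tried.

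**Follow-up visit.** No arithmetic applies. The flow chart has an eligibility review at Day 28-42; the Schedule and section 7.5 do not. The same flow-chart box also repeats past medical history, which the Schedule marks at baseline only. A list copied from the Day 0 box is therefore a plausible cause.

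**The case against.** **The Day 0 rule is ambiguous.** Section 4.1 names no qualifying visit, section 7.3 places the HARQ under eligibility at screening, and section 7.4 lists no eligibility review. The Day 0 mark could mean only a re-check of things that change, such as contraception or entry into another trial. This stands as far as it goes: the documents do not state outright that the Day 0 HARQ must reach 14. But two places put the full criteria at Day 0, none exempts HARQ, and section 4 makes failure of any criterion disqualifying. Staff could reasonably apply it.

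**The size is unknown and may be small.** This stands. If most referred patients score well above 14, the bias is negligible.

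**HARQ change is exploratory in an uncontrolled pilot.** This stands too, and limits the weight of the point. No symptom change here could be attributed to azithromycin with confidence. Still, p-values are planned, the pilot is meant to inform larger studies, and this source of bias is avoidable.

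**Stronger readings that the documents do not support:**
- *That responders are removed at follow-up.* A reader might infer this from the Day 28-42 flow-chart line together with section 13.3, which names as a ground for discontinuation "Ineligibility (either arising during the study or retrospective having been overlooked at screening"). But no passage says that a follow-up HARQ below 14 triggers anything, section 13.3 is discretionary, and section 4.4 keeps participants in follow-up unless they ask to withdraw fully.
- *That participants would fail the macrolide exclusion at follow-up.* This is doubtful: section 4 defines long-term azithromycin as more than 6 months, and they will have had 4 to 6 weeks.
- *That re-screening must be barred for HARQ.* Section 4.3 says: "Participants that fail screening can be re-screened (to a maximum of 3 times) if the reason for screen failure is resolved". With Day 0 thresholded, repeat attempts would enlarge the bias. Once Day 0 is ungated they add none to Day 0-to-follow-up change in this model, so no ban is needed.

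**Conclusion.** The point holds in limited form. As written, the eligibility review at Day 0 can truncate the HARQ baseline at 14 and produce an apparent improvement without any treatment effect. The spurious fall is about 0.8 to 2.0 points if the referred mean is 15 to 20, and 0.3 to 0.6 points at a mean of 30, given SD 12 to 13 and correlation 0.7 to 0.8. These inputs are assumptions; the protocol cannot fix the size. A screening-only rule brings the fall to about zero provided errors at screening and Day 0 are independent. If patients enter during a flare that lasts through both visits, some regression to the mean remains.

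The primary feasibility and acceptability outcomes are not biased in this way. The flow chart's follow-up entry is an inconsistency to correct and is not evidence that improving participants will be dropped.

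**What to change.** 1. In sections 4.1 and 6.3.1, state that the HARQ criterion is judged on the screening score only, and that the Day 0 HARQ is the analysis baseline and is not re-thresholded. Note beside the Day 0 eligibility entry in the Schedule and flow chart that it does not cover HARQ, and bring section 7.4 into line.
2. Reconcile the Day 28-42 flow-chart box with the Schedule and section 7.5 so that the HARQ criterion is not applied at follow-up.

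The cost is wording only: no added visits or data. The downside is that some entrants will have a Day 0 HARQ below 14. Under the assumptions above this is 13% to 24% at a mean of 15 to 20 (0.13 × 30 to 0.24 × 30, about 4 to 7 participants) and 5% to 6% at a mean of 30 (about 2 of 30). All would have qualified at screening. If the sponsor prefers to keep the Day 0 threshold, the protocol should acknowledge regression to the mean and treat HARQ change as descriptive.
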